### Statistical Analysis H1- H3

H1: FCGs participating in both intervention groups (Facebook and ACCESS) will report lower levels of anxiety (GAD-7), increased levels of pain knowledge (FPQ), and lower patient pain (BPI) compared to the EUC group at last follow-up.

H2: FCGs participating in the SDM process in team meeting will report lower levels of anxiety (GAD-7), increased levels of pain knowledge (FPQ), and lower patient pain (BPI) compared to either the Facebook-only group or the EUC group.

Drs. [name] and [name] will work with our statistical consultant [name] to examine differences between longitudinal profiles of the three study groups for each of the outcomes (GAD-7, FPQ, and patient pain). We will use mixed (hierarchical) models with repeated outcome measures nested within participants (see model below, where  $ij$  represents the  $i$ th observation of the  $j$ th participant). This will allow us to draw inferences about how outcome measures change through time (slope) between the three study groups. These models are able to accommodate differing numbers of measurements at varying time intervals for participants. As above, we will include covariates when indicated.

**Last post-baseline measure =  $\beta_0 + \beta_1[\text{study group}] + \beta_2[\text{baseline measure}] + \beta_3[\text{time since enrollment}]$**

H3: The effect of the intervention compared with EUC will be greater for those with lower (worse) anxiety scores at baseline. A multiple linear regression model will be used as for H1 above, but with an additional interaction term (study group X baseline GAD-7) to examine the modifying effect of baseline GAD-7 score. If the  $\beta_4$  coefficient is statistically significant, we will conclude that the effects of the ACCESS intervention are conditional on baseline perceptions:

**Qualitative Analysis** [name] will lead the analysis of qualitative data throughout the project. We will begin our initial coding from our preliminary work.

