We will test whether randomization created balanced groups by comparing baseline measures and demographic characteristics, using chi-square or t-test analysis for categorical or continuous variables, respectively. Variables that differ significantly between groups will be included in regression models as potential confounders. To compare outcomes for Hypotheses 1-4 (H1-H4), we will use the last available measure post-baseline and prior to death or the end of the study. The last available measurement typically represents the FCG's measure at the last point prior to the patient's death. This is a last observation analysis. Carpenter and Kenward argue that, in such analyses, time to this event should be taken into account. We will therefore include time from study enrollment to the last observation as a covariate. We will report estimates with 95% confidence intervals. To draw inferences from our study to the likely benefit to an equivalent population where the intervention under trial is a model of service delivery, all analyses of outcomes will be by intention-to-treat. The intention-to-treat analysis, consistent with the objectives of a pragmatic trial, will minimize the influence of "informative missingness" of the data and preserve groups' comparability.

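### GAD-7 under H1 and H2 is given two analyses, a last-observation comparison and a repeated-measures slope model, and the plan does not say which one decides

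*Combined protocol and SAP*

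**What the plan says.** The list under Quantitative and Qualitative Measures makes GAD-7 the primary outcome. Two descriptions of its analysis follow.

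**Last observation.** For H1 to H4, the Statistical Analysis section says "we will use the last available measure post-baseline and prior to death or the end of the study" and labels the approach: "This is a last observation analysis". Time from enrolment to that observation is a covariate, as is any variable found to differ between groups at baseline. The opening paragraph of that section also says that the final measure before the patient's death is analysed. In Statistical Analysis H1-H3, three things fit this description:
- H1 is worded as a comparison with enhanced usual care (EUC): "compared to the EUC group at last follow-up".
- The displayed equation has "Last post-baseline measure" as its outcome, with study group, baseline measure and time since enrolment on the right-hand side.
- H3 looks back to H1 in these words: "A multiple linear regression model will be used as for H1 above, but with an additional interaction term".

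**Repeated measures.** The paragraph that follows H1 and H2 names GAD-7, pain knowledge and patient pain, and sets out to "examine differences between longitudinal profiles of the three study groups for each of the outcomes". It continues: "We will use mixed (hierarchical) models with repeated outcome measures nested within participants". The stated purpose is: "This will allow us to draw inferences about how outcome measures change through time (slope) between the three study groups". It points to a model below, indexed by observation and participant, and says that such models cope with differing numbers of measurements at varying intervals.

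Neither analysis is called primary, secondary, supportive or sensitivity. The word primary is attached only to the outcome.

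**The concern.** A group difference in the last recorded value and a group difference in slope answer different questions, and they are on different scales (points, and points per unit of time). Followed literally, the plan produces both for the primary outcome under the same hypotheses, and nothing says which result settles H1 or H2. An analyst could not tell from the text which model to report as the main one, and a reader of the results could not check that the choice was made in advance.

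**Working it through.** The documents state no power calculation, SD, effect size or intraclass correlation, so there is no figure to reproduce. The finding rests on steps 1 and 2. Steps 3 and 4 are illustrations with assumed inputs.

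**1. The two descriptions side by side**

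| | Last observation | Repeated measures |
|---|---|---|
| Where | Statistical Analysis; H1 wording; displayed equation; H3 | Paragraph after H1 and H2 |
| Data per caregiver | One value | All visits |
| Role of time | Covariate | Dimension of the outcome |
| Target | Group difference in last value | Group difference in slope |
| Status stated | None | None |

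The Statistical Analysis section names time to last observation as a covariate. The baseline measure as a routine term appears only in the displayed equation.

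**2. Can the displayed equation deliver a slope comparison?**
It reads: last value = β0 + β1·group + β2·baseline + β3·time. The change in expected outcome per unit of time is β3 in every group, so the difference in slope between groups is β3 − β3 = 0 by construction. A slope comparison needs group-by-time terms, and with three groups there are two of them. The equation also has no observation index and no participant random effect.

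**3. How far apart the two targets can be**
Assumed effects, used only to show scale:
- *Constant benefit of 1.5 points from the first follow-up visit.* The last-value difference is −1.5 whenever the last visit falls. The difference in post-baseline slope is 0. If day 0 enters the slope model, some slope appears, by an amount that depends on how baseline is handled.
- *Benefit growing by 1.5 points per 60 days.* The slope difference is −1.5/60 = −0.025 per day. The last-value difference depends on the day of the last visit: −0.025 × 14 = −0.35, × 30 = −0.75, × 60 = −1.5, × 90 = −2.25, × 120 = −3.0.

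In Study Statistics, the team's experience is that 75% of caregivers had left after 90 days. Last values would therefore come from widely differing follow-up times, and the two targets would not coincide.

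**4. Error rate if either test could be claimed**
Alpha is not stated. Two-sided 0.05 is assumed from the planned 95% intervals.
- P(either) = α1 + α2 − P(both). At 0.05 each, independent tests give 1 − 0.95² = 0.0975. Complete overlap gives 0.05, and the ceiling is 0.10.
- *Two-arm simulation, no effect.* 642/3 = 214 per arm (642 is the interview count in Qualitative Data), between-person SD 3.5, residual SD 3, about 75% gone by day 90, 200 runs. The last-value regression rejected in 5.5% of runs, the slope test in 4.5%, and either in 8.5%. Monte Carlo standard error: √(0.085 × 0.915/200) ≈ 0.02.
- *Three-arm cluster cross-over simulation, no effect.* Six hospices × three periods = 18 hospice-periods; 642/18 ≈ 36 caregivers in each; assumed arm sequences; SD 5; correlation 0.6; hospice-period variance 0%, 1% or 5% of total; 5,000 trials per setting. Both tests carried hospice, period and arm terms: 18 − (1 + 5 + 2 + 2) = 8 df. For both intervention groups against EUC, either test was significant in 8.1% to 10.1% of trials across three ways of building the slope model. Over correlations 0.5 to 0.7 the range was 7.7% to 10.5%. Single tests ran at 4.3% to 5.8%, which is how the upper end slightly exceeds 10%.

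**The case against.** The strongest reply is that the plan has in effect chosen. The general rule for H1 to H4 is the last available measure, and H1's wording, the displayed equation and H3's back-reference all agree with it. The mixed-model paragraph speaks of examining longitudinal profiles, which can be read as supporting work. The lean is real. It remains an inference, because the one model sentence written specifically for H1 and H2 commits to the mixed model in equally definite terms.

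A second reply is that the mismatch between paragraph and equation may come from PDF extraction. The text defines an index that appears in no displayed equation, H3 cites a β4 that is not shown, and H3 ends on a colon with nothing after it. So one should not conclude that the sponsor printed the wrong model. A recovered mixed-model equation would, however, leave two complete models with no ranking.

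A third reply is that harm requires someone to claim success on whichever test is significant, and no passage announces that. This stands, and it limits the severity.

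**Conclusion.** The point holds on the text alone: there are two estimands for the primary outcome under H1 and H2, neither is ranked, and the displayed equation cannot support the promised slope inference. It should be fixed before analysis, as a wording-level correction.

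Two stronger readings are tempting and are not supported. A reader might infer that the plan already inflates the type I error. It does not: the rate of about 8% to 10% applies only if success is claimed on either test, which the plan neither proposes nor rules out. That figure also rests on assumed SDs, correlations and exit patterns and, in the cluster version, on assumed sequences and on hospice and period terms that neither written analysis contains. A reader might also infer that the two analyses would often reach opposite conclusions in this trial. How often they would differ depends so heavily on the assumed effect size, SD and form of slope model that the documents support no figure.

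**What to change.** Before analysis:

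1. Name one model as primary for GAD-7 and label the other secondary or sensitivity.
2. State the contrasts separately. H1: both intervention groups against EUC. H2: Group 3 against Group 2, and Group 3 against EUC. One contrast cannot serve both hypotheses.
3. Print an equation that matches the chosen model, after checking the source file for any equation lost from the public copy.

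*Least change.* Make the last-observation regression (group, baseline, time to last observation) primary. State that the mixed model for slopes is secondary, and give it its own equation.

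*Alternative.* Make the mixed model primary. Print an equation indexed by observation and participant, with group, time, the two group-by-time terms and a participant random effect. Then edit both last-measure statements in Statistical Analysis, H1's reference to last follow-up, and H3's back-reference.

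Under either choice, the primary equation should not stay exactly as displayed. The Abstract and Randomization sections describe a cluster cross-over, so it needs hospice and hospice-period terms. Hospice-period should enter as a random effect, because arm is constant within a hospice-period and a full set of fixed terms would absorb it.

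The cost is wording only, since every measure is already scheduled. The downside is that one analysis loses headline status. The alternative needs edits in more places.

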### Qualitative Data

Video-recording: We will record 100% of all care plan meeting days with the web- conferencing intervention participants and 100% of meetings where all group participants are discussed for comparison using qualitative analysis until June 10, 2020 Facebook posts: We will also maintain 100% of the Facebook conversations for analysis and track all “likes” noted on posts. FCG Interviews: We will interview 100% of all FCGs in each group (total of 642 interviews) 14-21 days following their patient’s death. The interviews will be semi-structured based on guides developed in our preliminary work (see Appendix) and will include a post GAD-7 measure to evaluate post-care stress. Staff surveys: convenience sample annually by REDCap and distributed through the hospice sites email using the LEED questionnaire.

### Risks

Human subjects will incur minimal risk by participating in the study. Potential risks could include frustration or anxiety with learning new skills or malfunctioning or technically deficient equipment. Some individuals might be nervous having a ‘camera’ in the home despite their ability to control when it is on and off. As in most studies, despite efforts to protect confidentiality, potential exists for a privacy breach that could cause distress or embarrassment. All paper forms ????? and computerized data will be stored in secure environments to minimize this possibility. Finally, there is a potential for frustration about having additional activities to manage. We will continue to minimize these risks by being considerate as we contact family caregivers by phone and/or email to schedule activities. We also assure patients, both verbally and in writing, that they may withdraw from the study at any time. Finally, the hospice admissions nurse will not release names of any patients or FCGs to the research team without first allowing them to ‘opt out’ of the study. Once referrals are obtained, the Research Specialist will then call the family to assure convenience and interest in the study.

We have chosen the videoconferencing solution called VSee (Vsee Inc, Sunnyvale, CA), which is free to download and use for both personal and commercial use (similar to Skype). While both Skype and VSee are free videoconferencing systems, VSee is considered more secure. VSee uses open industry standard—FIPS 140-2 compliant 256-bit AES encryption—on all control and media traffic. Unlike Skype, VSee uses RSA public/private key to exchange the AES session key such that the VSee servers do not have access to the AES session key. This means only the people participating in a conversation can decrypt data passed through VSee conversations (whereas Skype has the ability to monitor individual conversations). For this reason, VSee is often referred to as a “telemedicine” videoconferencing tool and has been endorsed by numerous health care systems and organizations as a videoconferencing tool throughout the country (including Stanford Hospitals and Clinics, Trinity Health, Intermountain Healthcare etc.) (<http://vsee.com>). In a study by the Office of High Performance Computing and Communications at the NIH National Library of Medicine, investigators concluded that “VSee provided secure encrypted video that looked superior to other low-band width products.”

The Facebook platform requires special considerations of risk and privacy. The consent form ????? will make these issues known, and the protocol will require research staff to review participants' privacy settings (we recommend the strictest settings). They will be told that if they agree to participate in this study, their name will be added to a "closed secret" Facebook page, giving them access to other hospice FCGs enrolled in the study. Although the research team controls membership in this group, which is not available to the general public, participants will be advised to protect their personal information and privacy with their individual privacy settings. Members of the Facebook group may contact one another through the Facebook website. However, the research team will not share participants' personal contact information. To participate in the study, participants must join Facebook and have an account. They will be advised to read the Facebook privacy policy and set their Facebook privacy settings with the tightest controls. Our research staff will walk them through the privacy settings to assist in understanding their meaning. However, participants will decide on their Facebook privacy settings. They will be told that the settings of other group members might impact the privacy of what they share. They will also be informed of the Facebook policy that Facebook owns all materials placed on the Facebook website, and they will be advised to read the policy carefully if posting photos.

Likewise, we will tell FCGs that, as members of the secret Facebook group, they will be able to discuss experiences, share caregiving advice, and access questions and concerns regarding similar issues with others enrolled in the study. Each week, the research staff will provide a new information posting and discussion prompt. We will tell participants that nothing is required of them and that they may log into the site and read and respond (or not respond) to the discussion as they choose. Our research team will supply discussion information and review all comments and responses to determine the needs of members and the helpfulness of the Facebook page for FCGs.

Participants will be given a Rules of Conduct document outlining the ethical conduct expected of participants of this Facebook group (see Appendix). These rules include items like not giving medical advice to other FCGs and not being critical of other FCGs. If a participant does not follow these rules, the research staff can speak privately with them and, if necessary, after consultation with the Principal Investigator and research team, revoke their access to the page. The need for this never occurred in our pilot studies.

This Facebook group does not replace hospice services. Neither the research staff nor any member of the Facebook group will provide mental health services such as counseling. If the research staff becomes concerned about a caregiver's mental well-being, they will contact the hospice social worker to assure the safety of the caregiver and others.

### Adequacy of Protection against Risks

**Recruitment and Informed Consent:** Initial recruitment of subjects will take place through the hospice agency. Hospice staff, in compliance with privacy and confidentiality regulations, will screen eligible participants. The staff will briefly explain the study to families, provide an informational flyer, and document if a family chooses to 'opt-out' of the study. After a referral is supplied, the Research Specialist will call to explain the research process in detail. A waiver of consent will be reviewed with every patient and family member who is interested in participating, and will be emailed to them if they choose to participate. The Research Specialist will also explain the waiver of consent form to hospice staff. The form contains detailed information about the purpose of the study and contact information for the University of Missouri Health Sciences Institutional Review Board (MUHSIRB). The waiver of consent form emphasizes that the caregiver can discontinue study participation at any time, and that refusal or termination of participation will not affect the patient or caregivers relationship to the hospice agency or the quality of care delivered.

## Protection against Risk

Caregiver confidentiality and comfort with the technology are protected, for they must agree to use the video component of the web-conferencing. Our web conferencing software is encrypted, and access is password-protected. Caregivers are “called” by the Research Specialist to gain entry into the conference. We used this technology in our preliminary trial with no privacy issues.

Training staff to understand their role in preventing a breach will address protection of data confidentiality. All paper forms and recordings will be kept in locked cabinets in locked offices within a locked suite. All computerized data will be stored on password-protected and encrypted computers and networks. Only study personnel with a specific need to use data will be granted permission to access it. Finally, all patient/family information provided by the caregiver or the hospice will be identified with an arbitrary identification code rather than a name. For meetings that are video recorded, FCGs’ and patients’ full names will be edited from the video. All research data that leave the hospice office will be maintained in a locked file cabinet and secure computer in the PI’s office. It is anticipated that referral information will be scanned and emailed directly through the hospice site to Research Specialists within the hospice email system, eliminating potential breach of confidentiality via mail or by “crossing” encrypted email systems.

## Benefits

The proposed project has the potential to improve hospice services by allowing patients and their family caregivers better access to, and participation in, their hospice care. The Internet, telephone and social media platforms are tools that allow patients and families to participate in their team care plan discussions, and express their concerns, goals, and values as the care plan evolves. The social media platforms allow FCGs to obtain additional information and social support to improve the hospice experience.

### Importance of the Knowledge to be Gained

This project will evaluate the value to FCGs not only of participating formally in team care plan meetings to help shape their end-of-life plan, but also of receiving enhanced information and social support through social media. The underlying concept is that technology can aid patients and FCGs in joining discussions about their needs and help assure that their care plan fulfills those needs. With knowledge from this study, we will develop a plan to translate the intervention into hospice practice, and we will advocate that policy governing hospice care include such patient/family participation as usual care. Because hospices serve more than 1.5 million individuals annually improving the quality of life of FCGs would have a significant impact.

## Payment and Remuneration

Hospice Staff: All hospice staff at each participating site will receive \$30 check for the REDCap completion of the LEED survey. At the end of the survey they will be asked to supply their name, address, and social security number for payment. .

Hospice Caregivers will each receive \$50 for their effort in participating in the study.

## Costs

There is no cost to participants who participate in this study other than the use of their Internet enabled device, cell phone and Internet plan. If a participant does not have an Internet enabled

device or a cell phone/Internet plan which allows them to enroll or participate the grant will provide a smartphone at no charge to the participant.

## **Single Site IRB: WUSTL Reliance on MU**

MU will remain the single site for IRB when [name] transfers to [name] University (WUSTL). Effective October 1, 2020 [name] will become the PI overseeing the project through the MUIRB. [name] will file a Request to Rely with WUSTL IRB and the agreement will fall under the institutions master reliance agreement.

